8.4 Planned analyses

The main statistical analysis is planned when

- The planned number of patients have reached two years follow-up from date of randomization, and
- All data have been entered, verified and validated according to the data management plan

Prior to the main statistical analysis, the data base will be locked for further entering or altering of data. A separate statistical analysis plan (SAP) will provide further details on the planned statistical analyses. The SAP will be finalized, signed and dated prior to database lock.

Deviation from the original statistical plan will be described and justified in the Clinical Study Report.

8.5 Statistical Analysis

8.5.1 Primary analysis

- Primary variable: Overall survival at 2 years from randomization
- Assessment: From the electronic medical records (EPJ)
- Metric: Hazard ratio
- When the last recruited patient has reached two years follow-up or censor.

The primary analysis will be done by Cox regression with treatment group as covariate, adjusted for stratification factors in the randomization.

Primary population: By intention-to-treat (ITT), i.e. all randomized patients regardless of protocol adherence.

The treatment effect will be presented as hazard ratios between the two treatment groups and the standard of care group, in addition to 95% confidence intervals.

The null hypothesis to be tested is that there is no difference between the treatment groups on overall survival after 2 year. If the null hypothesis is rejected on a 5% significance level, the pairwise treatment group's differences will be tested on the 5% level with the family-wise error rate sustained by the closed test principle.

There will be no handling of missing values. All patients will be followed-up until 2 years or death of any reason. Patients lost to follow-up will be censored at time of last observation, and handled accordingly.

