8 STATISTICAL METHODS AND DATA ANALYSIS

8.1 Determination of Sample Size

We estimate an overall survival at two years in the standard care group (group 3) to be 30 %. We aim to decide whether the use of HAI (group 2) can increase this to 75 % and if liver-TX (group 3) can increase this to 90 %. For a two-sided parallel-group test of proportions to answer both questions with a power of 0.80 and an alpha of 0.05, this will require 16 completed patients per group 3 and 2 to show superiority for HAI over standard care (systemic chemotherapy). An additional 7 patients is needed in the transplant group (1) to show superiority over standard care group (3), bringing the total to 39 patients. This is based on a three-year accrual time, and a total of five-year follow-up from the first patient, ensuring at least two years follow-up for all patients. The trial is not powered to show a difference between group 2 and 1. Adding 15 % to allow for drop-outs, we aim to randomise a total of $18 + 18 + 9 = 45$ patients in a 2:2:1 ratio.

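### The primary Cox hazard ratio for transplant against control has a 39% chance of no finite estimate under the plan's own assumptions, and the protocol names no test or interval that copes with this

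*Protocol*

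**What the plan says.** Protocol section 8.5.1 names overall survival at two years as the primary variable and the hazard ratio as its metric. It states: "The primary analysis will be done by Cox regression with treatment group as covariate, adjusted for stratification factors in the randomization". Each experimental group is compared with standard of care, with 95% confidence intervals, in the intention-to-treat population. Patients are followed to two years or death. A global test comes first, then pairwise tests under the closed testing principle. The section gives no test statistic, no interval type and no rule for an arm without deaths.

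Protocol section 8.1 supplies the planning values. For control: "We estimate an overall survival at two years in the standard care group (group 3) to be 30" per cent. For HAI: "We aim to decide whether the use of HAI (group 2) can increase this to 75" per cent. For transplant: "if liver-TX (group 3) can increase this to 90" per cent (the group number is a slip, since transplant is group 1 elsewhere). The trial is sized by a comparison of proportions and not by a hazard ratio: "For a two-sided parallel-group test of proportions to answer both questions with a power of 0.80 and an alpha of 0.05". The result is 16 completers in each of HAI and control and 7 in transplant. With the drop-out allowance this becomes 18, 18 and 9 randomised.

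Section 8.4 leaves further analysis detail to a separate SAP, to be finalised before database lock.

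**The concern.** A Cox hazard ratio is estimated from events. If one arm has none, the partial likelihood keeps rising as that arm's log hazard ratio falls. The estimate then runs to a hazard ratio of zero, the standard error becomes enormous, and a Wald p-value approaches 1 however strongly the data favour that arm. Adjustment for stratification factors does not cure this, because no covariate gives an event to an arm that has none.

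The chosen metric and the planned effect therefore fit badly together for one of the two primary comparisons. What is at stake is the transplant conclusion. With no deaths among 9 transplant patients and 13 among 18 controls, Fisher's exact two-sided p is about 0.0006, yet a Wald test from the Cox model would be non-significant. The trial is open label at a single centre. By the time the SAP must be final, the team will know whether any of about nine transplant patients has died. A test chosen then could decide the result after the fact.

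**Working it through.** **Inputs (section 8.1).** Two-year survival 30% control, 75% HAI, 90% transplant; two-sided alpha 0.05; power 0.80; 16 + 16 + 7 completers; 18 + 18 + 9 randomised. From section 8.5.1: follow-up to two years or death.

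**Reproducing the plan's figure.** Unpooled formula: n per group = (1.96 + 0.8416)² × [p1(1−p1) + p2(1−p2)] / (p1−p2)².
- 30% v 75%: 7.849 × (0.21 + 0.1875) / 0.2025 = 15.41, so 16.
- 30% v 90%: 7.849 × (0.21 + 0.09) / 0.36 = 6.54, so 7.
- Total 16 + 16 + 7 = 39; 39 × 1.15 = 44.85, so 45.

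The plan's sample size is reproduced.

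**Expected deaths by two years.** Control 18 × 0.70 = 12.6; HAI 18 × 0.25 = 4.5; transplant 9 × 0.10 = 0.9. Total 18.

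**Chance of no deaths in an arm** = (two-year survival)^n.
- Transplant, 9 randomised: 0.9^9 = 0.387.
- Transplant, 7 completers: 0.9^7 = 0.478.
- HAI, 18 randomised: 0.75^18 = 0.006.

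**Sensitivity, transplant arm.**

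| Change | P(no deaths) |
|---|---|
| 9 patients, 15% lost uniformly over two years | 0.417 |
| 9 patients, true survival 95% | 0.630 |
| 9 patients, true survival 85% | 0.232 |
| 9 patients, true survival 80% | 0.134 |
| 12 patients, 90% | 0.282 |
| 15 patients, 90% | 0.206 |
| 9 patients, 90%, all follow-up of 2 to 5 years used (exponential survival, uniform accrual) | 0.192 |

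The larger arms are shown because section 8.2.1 allocates 1:1:1 within Excalibur 1, so the transplant arm's size depends on how many patients enter that part.

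**What happens in such a trial.** Simulation of 1,500 three-arm trials (18/18/9, exponential survival at 30/75/90%, censoring at two years, Cox model with treatment only):
- No transplant deaths in 37.9% of trials. In these, Wald rejects transplant v control in 0% (median standard error of the log hazard ratio about 550). The likelihood-ratio test rejects both the global null and transplant v control in 100%. The profile-likelihood upper 95% limit for the hazard ratio has median 0.20 (5th to 95th percentile 0.12 to 0.35).
- At least one transplant death: Wald rejects in 71%, likelihood ratio in 87%. With exactly one death (38% of trials), 82% and 97%.
- Combined: Wald 0.379 × 0 + 0.621 × 0.707 = 0.44; likelihood ratio 0.379 × 1 + 0.621 × 0.870 = 0.92.

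Separate two-group simulations at 30% v 90%, pairwise test alone:

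| Transplant v control | Wald | Likelihood ratio |
|---|---|---|
| 9 v 18 (all controls) | 0.42 | 0.90 |
| 9 v 9 | 0.34 | 0.82 |
| 7 v 16 (completers) | 0.20 | 0.86 |

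The ordinary likelihood-ratio test rejected in 5.0 to 5.5% of trials under the null. A Firth-penalised likelihood-ratio test gave power 0.91, 0.81 and 0.80 in the same three settings, with null rejection of 4.3 to 4.5%.

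**The case against.** The strongest reply is that the protocol never says Wald. It names Cox regression, hazard ratios and intervals, and the choice of test and interval is what a SAP commonly settles. The low power figures rest on a default that the document does not prescribe. This stands: those figures are conditional on that default. It also stands that the specified Cox model keeps its power if the likelihood-ratio test is used, so Firth penalisation is one option and not a necessity.

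The reply does not remove the point. The hazard ratio as primary metric is fixed in the protocol itself, and with no transplant deaths it has no finite estimate on the log scale whichever test is chosen.

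The scope is also limited. HAI v control is essentially untouched, the global likelihood-ratio test works, and section 1.7 describes the transplant arm as mainly proof of principle.

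A reader might infer that the primary analysis fails exactly when transplant works. The documents do not support that. At 90% survival, 61% of trials have at least one transplant death and a finite hazard ratio. At 80% survival, still far above 30%, the chance of no deaths is 13%. Even with no deaths, a profile interval has an informative upper limit. A reader might also infer that covariate adjustment makes matters worse. No adjusted calculation was run, so that is not claimed.

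**Conclusion.** The point holds in a limited form. On the plan's own inputs there is a 39% chance (48% with 7 completers) that the primary metric has no finite estimate for transplant v control and that Wald inference on it is useless. With the test left open, power for that comparison is about 0.42 under Wald and about 0.90 under the likelihood-ratio test at 9 v 18, against the planned 0.80.

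The 39% assumes 9 transplant patients, 90% survival and censoring at two years. Over the alternatives tabulated it ranges from 13% to 63%. The power figures further assume exponential survival, no loss to follow-up and no covariate adjustment. This is a badly fixed choice with an inexpensive remedy; it does not make the primary analysis invalid.

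**What to change.** Amend section 8.5.1, before outcomes accrue, as follows:
- Take the global and pairwise p-values from the likelihood-ratio test of the Cox model, or from a permutation log-rank test, and not from Wald statistics.
- Report hazard ratios with profile-likelihood intervals, or with Firth-penalised estimates and intervals. With unpenalised profile likelihood and no deaths in an arm, state that the estimate is zero and give the upper limit.
- Report two-year survival per arm and the difference from control. These match the endpoint and the sample-size basis, and stay defined without deaths. Use an exact or score-type interval: the Greenwood variance is zero in an arm with no deaths, so the usual Kaplan-Meier interval breaks down in the same situation.

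The cost is one paragraph of text, standard software and slightly more analysis work. Firth penalisation would shrink the hazard ratios slightly, including the one for HAI.

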3 OVERALL STUDY DESIGN/OVERVIEW OF DESIGN

EXCALIBUR is a phase II study.

Excalibur 1 is a three-armed RCT comparing 2nd line systemic chemotherapy to liver transplant and to HAI. Because of the transplant arm, this sub-trial has somewhat stricter inclusion criteria.

Excalibur 2 is a two-armed RCT conducted within the same framework as *Excalibur 1*, but without the transplant arm, and with somewhat wider inclusion criteria (see figure). For analysis, the HAI arm and the systemic chemotherapy arm of *Excalibur 1* and 2 will be directly comparable (stratified for age and primary tumour resected/in situ) and hence boost numbers for this comparison.

[figure not shown]
Study period:

Estimated date of first patient enrolled: February 2021

Anticipated recruitment period: 3 years

Estimated date of last patient completed: November 2024

Treatment duration: up to 2 years

- HAI (intervention group 2) and Systemic therapy (control arm, group 3): Until progression or resection, up to two years
- Transplant (intervention group 1): Until transplant or until removal from list.

Follow-up for outcomes: 10 years

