5.5 Schedule of events

- Identification
 - Patients are identified from referrals or during MDT-meetings by surgeon or oncologist.
 - A trial specific MDT evaluation of liver metastases and resectability is performed.
 - Following this MDT-meeting, the patient is invited for out-patient visit within 10 days.
 - If no updated high-quality thoracic/abdominal CT and MR scan is available (No older than 4 weeks by date of out-patient visit), these are booked.
- At out patient clinic:
 - Eligibility for *Excalibur* 1 or 2 is assessed.
 - In house review of new images if applicable.
 - Eligible patients receive written and oral information about the trial and risks pertaining to HAI-catheter insertion/transplant/systemic chemotherapy
 - Measurement of CEA and standard blood chemistry
 - If patient consents:
 - Baseline QoL survey (C30) and EQ5D questionnaire is completed
 - Patient's latest CT or MRI scans are referred to next MDT meeting for designation of three target lesions for RECIST evaluation
 - Availability of mutation status is confirmed. If mutation status is not already performed, this is ordered from pathology lab.
 - Decision of eligibility for *Excalibur* 1 or 2 is decided by two trial investigators. If a patient is found to be eligibility for *Excalibur* 1 a member of transplant team will concur and provide specific information about transplants.
 - If a patient has begun or is planned for 2nd line chemotherapy, the randomization MUST take place before any evaluation of 2nd line treatment effect, i.e imaging (CT/MR). (PET for evaluation of extra hepatic disease is allowed). The choice of drugs for 2nd line chemotherapy must be decided on prior to randomization.
 - Inclusion is confirmed
 - Patient card
 - The following appointments are booked within two weeks:
 - A PET scan following 4 week chemo abstinence. If the patient has recently received systemic chemotherapy, a 4 week chemo abstinence must be ensured and randomization may need to be somewhat delayed.
 - Patients eligible for *Excalibur* 1 for individual assessment by transplant team
 - An operation theatre for insertion of HAI-pump catheter at four weeks from inclusion
- PI meeting two weeks following inclusion:
 - Documents, inclusion details, transplant assessment and PET results are reviewed

- If satisfactory, a web-based randomization is performed.
- All patients:

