8.2 Randomization

8.2.1 Allocation-sequence generation

Randomized lists are generated for three groups in *Excalibur 1* in a 1:1:1 distribution and with a variable but unknown block-size of 3 or 6. Further, lists are generated for two groups in *Excalibur 2* in a 1:1 distribution. These will be generated and stored by personell not participating in the trial, and in offices physically removed from the clinical facilities.

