8.3 Population for Analysis

The following populations will be considered for the analyses:

- Intention to treat (ITT) population: All randomized participants, regardless of protocol adherence. The primary endpoint analysis will be performed on all subjects on an intention-to-treat basis.
- Per-protocol population (PP): Includes all subjects who have undergone the treatment for which they were allocated.
- Patients randomized to HAI-treatment or liver transplantation actually receiving these treatments'
- Safety population: Includes all subjects who have received at least one dose of study medication. Subjects who withdraw from the study will be included in the safety analysis. A list of withdrawn subjects, preferably with the reasons for withdrawal, will be made.
- Subgroups defined by: Left versus right sided primary tumour, degree of PET uptake in liver, FONG/Oslo-score

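### The primary Cox model adjusts only for the randomisation stratification factors and leaves out the Fong/Oslo score that section 8.3 already needs: a forgone gain of about 0 to 8 points of power, depending on how prognostic the score is

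*Protocol*

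**What the plan says.** Section 8.5.1 of the protocol fixes the covariates of the primary model: "The primary analysis will be done by Cox regression with treatment group as covariate, adjusted for stratification factors in the randomization". The analysis is by intention to treat, and the same section says that missing values will not be handled.

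The factors are named only in section 3, which describes the HAI and chemotherapy arms of the two sub-trials as comparable, "stratified for age and primary tumour resected/in situ". Section 8.2.1 names none: "Randomized lists are generated for three groups in *Excalibur 1* in a 1:1:1 distribution", with separate 1:1 lists for Excalibur 2. Inclusion criterion 1 in section 4.3.1 requires a radically resected primary.

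Section 8.3 lists, among the analysis populations, "Subgroups defined by: Left versus right sided primary tumour, degree of PET uptake in liver, FONG/Oslo-score". These variables have no other role in section 8. Section 5.5 places the relevant measurements before randomisation: "Measurement of CEA and standard blood chemistry" at the out-patient visit and, at the meeting that precedes web randomisation, "Documents, inclusion details, transplant assessment and PET results are reviewed".

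On prognostic strength the protocol is divided. Section 1.4 links left-sided tumours and absence of RAS or BRAF mutations to longer survival. Section 1.2 says that robust scoring systems with enough discriminatory power are lacking. No hazard ratio is given for any of these factors.

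**The concern.** The trial is small, and its stated adjustment set carries little information on tumour biology: age, plus a factor that eligibility nearly fixes. The score that the plan needs anyway serves only to divide 45 patients into subgroups holding very few deaths. As one continuous covariate in the primary model it would serve the main comparison.

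Two things are at stake. First, in a Cox model an omitted prognostic covariate pulls the hazard ratio towards 1 and costs power. Second, with 18 v 18 (and 18 v 9 for transplant) a chance difference between arms in baseline prognosis can move an unadjusted hazard ratio noticeably.

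This is more than a detail left to the SAP. Section 8.5.1 states the covariate set, so adding a score changes a stated rule.

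**Working it through.** **Inputs (section 8.1).** Two-year survival: control 30%, HAI 75%, transplant 90%. Two-sided alpha 0.05, power 0.80. Completed patients 16 + 16 + 7 = 39; randomised 18 + 18 + 9 = 45.

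**The plan's own figure.** Two proportions, unpooled variance: n = (1.96 + 0.84)² × (0.30×0.70 + 0.75×0.25) / 0.45² = 7.85 × 0.3975 / 0.2025 = 15.4, so 16 per arm. For 30% v 90%: 7.85 × (0.21 + 0.09) / 0.60² = 6.5, so 7. Then 39 × 1.15 = 44.9, so 45. The stated numbers reproduce.

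**Deaths by two years.** Control 18 × 0.70 = 12.6; HAI 18 × 0.25 = 4.5; transplant 9 × 0.10 = 0.9. That is 18.0 in all and 17.1 for HAI v control. A subgroup of one third of the patients would hold 4.2, 1.5 and 0.3 deaths.

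**Power of the Cox comparison without the score.** Exponential hazard ratio = ln 0.75 / ln 0.30 = 0.239. Schoenfeld's formula with 17.1 events gives 0.84. Simulation gives 0.81 to 0.84.

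**Effect of adding one score.** Simulated trials, 18 v 18: exponential survival, censoring at two years, marginal survival held at 30% v 75%, one standardised normal score, likelihood-ratio test at 5%. The strength of the score is an assumption in every row.

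| Assumed HR per SD (log-hazard SD) | Power without score | Power with score | Gain, points |
|---|---|---|---|
| 1.0 (0) | 0.81–0.82 | 0.81 | −1 to 0 |
| 1.3 (0.26) | 0.815 | 0.823 | +1 |
| 1.35 (0.3) | 0.81 | 0.83 | +2 |
| 1.5 (0.41) | 0.81 | 0.83–0.84 | +2 to +3 |
| 1.65 (0.5) | 0.83 | 0.87 | +4 |
| 1.8 (0.59) | 0.83 | 0.88 | +5 |
| 2.0 (0.69–0.7) | 0.82–0.84 | 0.90 | +6 to +8 |

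With 4,000 trials the standard error of a power near 0.82 is √(0.82 × 0.18 / 4000) = 0.006, so one-point differences between rows mean little.

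**Three arms, closed test, 18/18/9.** Power for HAI goes from 0.796 to 0.794 at HR 1.0, 0.803 to 0.812 at 1.3, 0.810 to 0.840 at 1.5, and 0.820 to 0.894 at 2.0. The pattern is the same.

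**More covariates.** With two uninformative covariates entered as well as the score, the gain at HR 2.0 is about 6 points (0.821 to 0.884).

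**Type I error.** In one set of runs it was 4.8 to 5.2% without and 5.2 to 5.6% with the score; in another, 4.9 to 6.0% and 5.3 to 6.6%. The rise is at most about 1 point.

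**Chance imbalance.** The difference in arm means of a standardised score has standard error √(1/18 + 1/18) = 0.33 SD for 18 v 18 and √(1/18 + 1/9) = 0.41 SD for 18 v 9. An imbalance of one standard error at 18 v 18 multiplies an unadjusted hazard ratio by about exp(0.5 × 0.333) = 1.18 if the log-hazard SD is 0.5, and exp(0.8 × 0.333) = 1.31 if it is 0.8. The chance of an imbalance above 0.5 SD is 13% at 18 v 18 and 22% at 18 v 9.

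**The case against.** The planned model is standard and valid. Adjusting for the randomisation factors contradicts nothing and miscalculates nothing, and section 8.4 leaves further detail to a SAP, where an adjusted sensitivity analysis could sit. That stands, and it is why the point is an improvement rather than a correction.

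The gain rests on an assumed prognostic strength, and section 1.2 speaks against a strong score. Eligibility (six or more metastases, failure of first-line treatment, ECOG 0 or 1) may narrow its spread further. This stands too. Section 1.2 does concern selecting patients for surgery, and a score too weak for that can still help as a covariate.

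The planned model may already hold prognostic information if the Excalibur 1 or 2 list counts as a stratification factor, since the sub-trials differ on BRAF, extrahepatic disease, lesion size and age. With one binary stratum assumed correlated with the score (latent correlation 0.7), adding the score gained 1, 3 and 5 points at log-hazard SD 0.4, 0.5 and 0.8. This reduces the gain without removing it.

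Chance imbalance is not bias; the confidence interval already allows for it. Adjustment deals with the imbalance actually seen.

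A reader might infer that tests in very small subgroups are planned and should be struck out. Sections 8.5.1 and 8.5.2 plan none. A reader might also infer that the score is ready to use. The protocol defines neither Fong nor Oslo and schedules no calculation of either.

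**Conclusion.** The point holds as a forgone gain. The primary model omits a baseline score that section 8.3 needs for every patient, and the adjustment set it does state is thin and not clearly defined. One prespecified score would add about 0 to 2 points of power at an assumed hazard ratio per SD of 1.0 to 1.3, 2 to 4 at about 1.5 to 1.65, and 6 to 8 at about 2.0. It would also protect the estimate against an imbalance that, at one standard error, shifts the hazard ratio by a factor of about 1.18 to 1.31 (log-hazard SD 0.5 to 0.8).

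A reader might go further and conclude that the plan loses a known amount of power, or that the main comparison is underpowered. The documents support neither. They give no prognostic hazard ratio, so every figure for the gain is conditional, and a weak score gains almost nothing. At the rates in section 8.1, power without the score is already about 0.80 to 0.84.

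The figures assume proportional hazards with exponential survival, 18 patients per arm followed to death or two years, and a normally distributed score. The effect of the score on power for the transplant comparison, with 0.9 expected transplant deaths, was not simulated.

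**What to change.** In section 8.5.1, before any outcome data are seen:

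- Name one score, Fong or Oslo but not both, and define it.
- Compute it from pre-randomisation data for every randomised patient. Because 8.5.1 provides no handling of missing values, a missing score would drop that patient from the intention-to-treat model.
- Enter it as a single continuous covariate alongside the stratification factors. Do not also enter sidedness and PET uptake; if uninformative, further covariates give back part of the gain.
- Report the model without the score as a sensitivity analysis.

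In the same change, state which stratification factors are meant, reconciling section 3, inclusion criterion 1 and section 8.2. In section 8.3, a sentence that the subgroups are descriptive would make plain what the plan already implies.

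The cost is protocol or SAP wording and one calculation per patient. Statistically it is one more parameter with about 18 deaths: up to about 1 point of power lost if the score is uninformative, and up to about 1 point of type I error inflation with the asymptotic test.

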4. Non-curable pulmonary or peritoneal metastases, non-regional lymph-nodes, or local recurrence on PET/CT scan, and on CT or MRI thorax/abdomen/pelvis dated within 6 weeks prior to the trial hospital MDT meeting.
5. Patients with known intolerance or allergy to any ingredient of the IMP to be used as standard therapy for that patient must be excluded
6. Breastfeeding women must be excluded
7. Patients with a psychiatric condition that makes participation in the trial impossible or unethical
8. Patients in a poor nutritional state, those with depressed bone marrow function or those with potentially serious infections must be excluded.
9. Any other reason why, in the opinion of the investigators, the patient should not participate.

Exclusion Excalibur 1

Any of the following will preclude inclusion into Excalibur 1 (but not into Excalibur 2)

1. BRAF positivity
2. Any sign of extra-hepatic metastatic disease or local recurrence on PET/CT scan, and on CT or MRI thorax/abdomen/pelvis dated within 6 weeks prior to the trial hospital MDT meeting (exception allowed for ≤ 3 resectable lung lesions all ≤ 15 mm).
3. Liver lesion >10 cm
4. Patient BMI > 30
5. Any previous non colorectal malignancy within latest five years
6. Age ≥ 70 years

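### Transplant is compared with all standard-care controls, about half of whom could not have been randomised to transplant, and sub-trial is not named as an adjustment factor

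*Protocol*

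**What the plan says.** Section 3 describes two randomised sub-trials under one protocol. Excalibur 1 has three arms. Excalibur 2 drops the transplant arm and recruits "with somewhat wider inclusion criteria (see figure"). Section 8.2.1 gives each its own lists, 1:1:1 and 1:1.

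The difference in population is set out in section 4.3 under the Excalibur 1 exclusions: "Any of the following will preclude inclusion into Excalibur 1 (but not into Excalibur 2"). The list is BRAF positivity, signs of extrahepatic disease or local recurrence (with an exception for a few small resectable lung lesions), a liver lesion above 10 cm, BMI above 30, another malignancy in the last five years, and age 70 or more.

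Section 3 says that the HAI and systemic arms of the two sub-trials can be compared directly, stratified for age and for primary tumour resected or in situ. It makes no such statement for transplant.

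Section 8.1 nevertheless sizes the transplant arm against the whole control group: "An additional 7 patients is needed in the transplant group (1) to show superiority over standard care group (3"). Section 8.5.1 specifies a single Cox model on the full ITT population, adjusted for the randomisation's stratification factors, and "The treatment effect will be presented as hazard ratios between the two treatment groups and the standard of care group". A three-group null hypothesis is tested first. Pairwise tests follow under the closed test principle.

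**The concern.** Randomisation protects a contrast only among patients who could have received either treatment. Controls recruited through Excalibur 2 are there because they failed at least one Excalibur 1 criterion, so against transplant they are external controls. Some of those criteria probably carry a worse prognosis. Section 1.4 itself associates absence of (K)RAS or BRAF mutation with longer survival, and lesions above 10 cm point the same way.

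If Excalibur 2 controls die sooner, the pooled reference group looks worse than the proper comparator and transplant looks better than it is. This affects one of the two comparisons for which section 8.1 claims power. It also affects the global test that opens the closed procedure.

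**Working it through.** **Reproducing the plan's figures.** Inputs from section 8.1: "For a two-sided parallel-group test of proportions to answer both questions with a power of 0.80 and an alpha of 0.05"; 2-year survival of 30% on standard care, 75% with HAI and 90% with transplant. With unpooled variance, n per arm = (1.960 + 0.842)² × [p₁(1−p₁) + p₂(1−p₂)] / (p₁−p₂)².

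- HAI: 7.849 × (0.21 + 0.1875) / 0.45² = 15.4, so 16.
- Transplant: 7.849 × (0.21 + 0.09) / 0.60² = 6.54, so 7.
- Total: 16 + 16 + 7 = 39, and 39 × 1.15 = 44.85, so 45.

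The 7 is therefore the answer for 7 v 7, although the text sets it against a control group of 16.

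**Share of controls outside the transplant randomisation.** Nine transplant patients under 1:1:1 imply 9 Excalibur 1 controls. That leaves 18 − 9 = 9 of 18 (50%) from Excalibur 2. Among completers it is 16 − 7 = 9 of 16 (56%).

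**Which factors are adjusted for.** Section 8.5.1 refers to stratification factors, but section 8.2 names none. Section 3 names age and primary resected or in situ. Inclusion criterion 1a requires a radically resected primary, so the second should hardly vary. Age corresponds to one of the six Excalibur 1 exclusions. BRAF status, lesion size and sub-trial are not named.

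**Size of the bias under assumed survival.** The documents give no survival by sub-trial, so the following are assumptions: exponential survival, censoring at 24 months, average control 2-year survival of 30%, no transplant effect, equal numbers of controls from each sub-trial. With S₁ and S₂ the 2-year survival in Excalibur 1 and 2, λ = −ln(S)/24, and the pooled control rate is [(1−S₁) + (1−S₂)] / [(1−S₁)/λ₁ + (1−S₂)/λ₂].

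For 40/20%: λ₁ = 0.0382, λ₂ = 0.0671, pooled rate = 1.4 / (15.7 + 11.9) = 0.0506, ratio = 0.0382 / 0.0506 = 0.75. The same steps give the other rows. The error rates are simulated for 9 transplant patients v 9 + 9 controls by log-rank test.

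| Excalibur 1/2 survival | Spurious ratio | Pairwise two-sided error | After global test, HAI ineffective | After global test, HAI as planned |
|---|---|---|---|---|
| 40/20% | 0.75 | 7–8% | about 3% | about 8% |
| 45/15% | 0.65 | 10–11% | about 6% | about 10% |
| 50/10% | 0.55 | 15–16% | 7–8% | about 16% |

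A large-sample Cox fit gives 0.75, 0.65 and 0.56, and 0.87 for a milder 35/25% gap. Nearly all of the error favours transplant: 6.8%, 9.9% and 15.7% against a nominal 2.5% in that direction. With sub-trial as a covariate the hazard ratio returns to 0.98–1.01. Stratifying by sub-trial brings the two-sided error back to about 5%.

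**Transplant power, 30% v 90%.** Unpooled formula: Φ(0.60 / √(0.21/n₁ + 0.09/n₂) − 1.96).

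| Controls v transplant | Unpooled formula | Pooled variance | Fisher | Log-rank |
|---|---|---|---|---|
| 18 v 9 (both sub-trials) | 0.98 | 0.91 | 0.89 | about 0.9 |
| 9 v 9 (Excalibur 1) | 0.91 | 0.79 | 0.67 | about 0.80 |
| 7 v 7 (Excalibur 1 completers) | 0.83 | 0.66 | 0.44 | about 0.67 |

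If Excalibur 1 controls reach 45% at two years, log-rank power at 9 v 9 is about 0.57.

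**The case against.** The strongest reply is that the protocol may already contain the remedy. The only separation of lists described in section 8.2 is by sub-trial, so the stratification factors in section 8.5.1 could be read to include it, and a SAP could say so. That would remove most of the bias. The reply stands in part: pooling for transplant follows from the single reference group and the full ITT population, and no sentence states it outright. But the protocol does not name sub-trial, and the factors it does name do not stand in for it.

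Three further points stand.

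- A reader might infer from the Excalibur 1 exclusions that Excalibur 2 is open to extrahepatic disease generally. The criteria common to both sub-trials do not support that. Past extrahepatic lesions must have been treated successfully more than two years ago. Non-curable lung or peritoneal disease, non-regional nodes and local recurrence exclude from both. Excalibur 1 itself tolerates a few small lung lesions. BMI and earlier malignancy have no stated prognostic direction.
- The survival gaps are assumed, and 50/10% is extreme.
- The global test lowers the error if neither treatment works. It gives almost no protection if HAI works as planned, because the global test then tends to reject anyway.

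Section 1.7 describes the transplant arm as mainly proof of principle. That lowers the stakes, but the comparison is still powered and tested as primary.

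**Conclusion.** The concern holds conditionally. As sections 8.1 and 8.5.1 are written, about half of the transplant comparator group was never randomised against transplant. Unless sub-trial is among the adjustment factors, that contrast and the global test are partly non-randomised. The likely direction favours transplant, mainly through BRAF positivity and large lesions. This is an inference, and the size is unknown. The range above (spurious hazard ratio about 0.75 to 0.55) rests wholly on the assumed survival gaps.

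Two stronger readings are not supported. One is that the transplant comparison is certainly confounded, so that a positive result would reflect eligibility alone; the text leaves room for adjustment by sub-trial and gives no survival by sub-trial. The other is that the stated power of 0.80 simply survives a restriction to Excalibur 1 controls. By log-rank it does at 9 v 9 with 30% v 90%, but not at the 7 completers that section 8.1 plans on.

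HAI against standard care is randomised within both sub-trials and is not biased in this way.

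**What to change.** - In 8.2 and 8.5.1, name sub-trial as a stratification factor, and stratify both the Cox model and the global test by it. Transplant is then compared with standard care within Excalibur 1, and HAI with standard care within each sub-trial and combined. For the pairwise transplant test, fitting only the transplant and standard-care arms of Excalibur 1 avoids indirect borrowing through an HAI effect assumed common to both sub-trials.
- In 8.1, restate transplant power against concurrent Excalibur 1 controls at 30% v 90%: by log-rank about 0.80 at 9 v 9 and about 0.67 at 7 v 7 (0.91 and 0.83 by the plan's unpooled formula). State that it falls to about 0.57 at 9 v 9 if those controls reach 45%.

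The change needs no extra patients or data and can be made before database lock. The cost is lower transplant power than with pooled controls: by log-rank about 0.80 instead of about 0.9 at the randomised numbers. The extra power came partly from patients outside the transplant randomisation.
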